10.4. Statistic analysis

Associations between overall survival and progression-free survival with patients' baseline characteristics will be evaluated using the log-rank test.

The maximum relative risk value based on the log-rank test will be used to provide a quantitative summary of the data, with 95% confidence intervals. Median survival, time to progression, and associated 95% confidence intervals will be calculated. Kaplan-Meier curves will be constructed to show the estimated probabilities of overall survival and time to progression.

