4.2.3. Molecular biology of oligodendroglial tumors

Table 1 summarizes the current knowledge on the molecular and genetic alterations that are present in the development and progression of oligodendrogliomas. Deletions in chromosomes 1p and 19q (loss of heterozygosity, PH) are the most frequent and earliest alterations in the tumor progression of oligodendrogliomas. In fact, the frequency of PH 1p and 19q in WHO grade II oligodendrogliomas is 80-90%, while in anaplastic oligodendrogliomas it is 31-70%.⁵ In most cases, the losses of 1p and 19q are combined, and the mechanism of the associated loss of these two chromosomal portions is currently not known. In recent years, it has been determined that the loss of 1p/19q is closely associated with mutations in IDH1/2 and also with the existence of a methylator phenotype.

The transformation of a low-grade tumor into anaplastic oligodendrogloma occurs due to the accumulation of genetic alterations (Table 1). The most important are the deletions of 9p and 10q. These alterations were found in a small number of WHO grade II oligodendrogliomas, being much more common in grade III. The CDKN2A gene, which is located at 9p21, presents homozygous deletions in more than 1/3 of anaplastic oligodendrogliomas⁹⁻¹¹. It is also interesting that homozygous deletions of CDKN2A are particularly common in oligodendrogliomas that do not have loss of 1p and 19q. The suppressor genes CDKN2A and CDKN2B encode the proteins p16 (INK4a) and p15 (INK4b), respectively, whose function is to inhibit CDK4 and CDK6. Similar to what happens in astrocytomas, the pRb pathway is altered in a significant percentage of anaplastic oligodendrogliomas, either through homozygous deletion or hypermethylation of CDKN2A; the amplification and elevated expression of CDK4A; or hypermethylation and loss of pRb expression.

Figure 1. Most important genetic alterations in oligodendrogliomas⁵

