4.3.2. CDK4/6 in High Grade Gliomas

Genetic alterations affecting the CDK4/6-CyclinD-INK4-RB regulatory axis in gliomas are well documented.¹⁷ and have been corroborated in large-scale genetic analyzes^{18,19}. The most frequent alteration of this molecular pathway in glioblastomas is the homozygous deletion of the CDKN2A/B gene that encodes the p16 proteins.^{INK4a} the p15^{INK4B}, which affect more than 50% of this tumor line. Other alterations are amplification of CDK4 (15-20%) and homozygous deletion of RB1 (10%). Amplification of CDK6 and cyclins D as well as homozygous deletion of p18^{INK4c} They are less frequent.

Of all these alterations, only genetic inactivation of RB leads the tumor to be resistant to CDK4/6 inhibition. In fact, “in vitro” studies with PD0332991 against a panel of glioblastoma showed that all those with conservation of the RB protein were sensitive to the drug while the 5 cell lines with homozygous inactivation of RB were resistant to PD0332991.

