4.6.2. Secondary objectives

- To evaluate the safety and tolerability of oral administration of Palbociclib in patients with recurrent anaplastic oligodendrogliomas.
- Evaluate the antitumor response according to the RANO criteria
- Assess Global Survival (GS)
- To evaluate the duration of response in patients with an objective response.
- Assess changes in glucocorticoid use.
- Assess changes in neurological status
- To evaluate whether the following biomarkers are related to PFS and OS: deletions in CDKN2A, deletions in CDKN2B, CDK4 amplification, CDK6 amplification, cyclin D amplification.
- To evaluate whether the following biomarkers are related to the response rate: deletions in CDKN2A, CDKN2B deletions, CDK4 amplification, CDK6 amplification, Cyclin D amplification.

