10.3. Hypothesis

Clinical basis: historical data for the elaboration of the study hypothesis have been obtained from the analysis of a database containing 350 patients with recurrent high-grade gliomas (125 anaplastic gliomas) who were prospectively treated in phase II studies. The 6-month progression-free survival (PFS-6m) was 31% for anaplastic gliomas (Wong et al. J Clin Oncol 17:2572-2578). The authors acknowledge the limitation because in this study the results were analyzed for all anaplastic gliomas and not only anaplastic oligodendrogliomas. However, no further published data are available regarding the results in recurrent anaplastic oligodendrogliomas.

Null hypothesis (H0): $P \leq P_0$

Alternative hypothesis to test (H1): $P \geq P_1$

Assumptions:

P: probability of remaining alive and progression-free at 6 months

P_0 : 25%

P_1 : 45%

Expected profit: 20% (25% vs. 45%)

Type I error, $\alpha \leq 0.05$

Type II error, $\beta \geq 0.20$

Sample size: 40 patients

A benefit will be considered if 18/40 patients are alive and progression-free at 6 months.

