1.2.3. PREVIOUS PATHOLOGIES

For 9 patients (26.5%) previous pathologies were not reported. In those patients with previous pathologies, seizures were the most common (n=7, 17.6%) previous pathology.

Table 19. Previous pathologies

		N	%
Previous pathologies	No		
	Yes		
	Total		
Previous pathologies	(Indicate previous pathologies. Exemples:		
	Fatigue		
	Cognitive disturbance		
	Muscle weakness left-sided		
		

Table 20. List of previous pathologies

Pat. n.	Hospital	Previous pathology	Intensity	Action
1	01-003			
2	01-004			
3	01-006			
..	01-006			

Table 21. Time since diagnosis

	N	Mean	SD	Median	Min	Max
Time since 1st diagnosis until 1st cycle (months)						

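### Section 10.4's log-rank test is a poor fit for continuous baseline factors (it needs unstated cut-points and loses power) and for any biomarker with only 1-4 carriers (its asymptotic p-value can be too small)

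*Protocol*

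**What the plan says.** Section 10.4 of the protocol gives one method for relating OS and PFS to patient factors: associations with "baseline characteristics will be evaluated using the log-rank test". The effect summary is a relative risk derived from the same test, with a 95% interval. The section does not give a significance level for these tests, a choice between asymptotic and exact p-values, groupings, cut-points or a regression model. It does not mention biomarkers.

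Section 4.6.2 lists two biomarker objectives. The first reads "To evaluate whether the following biomarkers are related to PFS and OS" and names "deletions in CDKN2A, deletions in CDKN2B, CDK4 amplification, CDK6 amplification, cyclin D amplification". The second reads "To evaluate whether the following biomarkers are related to the response rate" for the same five markers. Response is not a time-to-event outcome, so the log-rank sentence cannot serve the second objective, and no other method is named for it.

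On marker frequency, section 4.2.3 puts homozygous CDKN2A deletion at more than a third of anaplastic oligodendrogliomas, but adds that "homozygous deletions of CDKN2A are particularly common in oligodendrogliomas that do not have loss of 1p and 19q". Section 6.1 requires 1p/19q co-deletion. Section 4.3.2, on glioblastoma, gives 15-20% for CDK4 amplification and describes as less frequent "Amplification of CDK6 and cyclins D as well as homozygous deletion of" p18.

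The SAP has no log-rank test and no biomarker table. It summarises continuous factors such as "Time since 1st diagnosis until 1st cycle (months" in Table 21. Its only test of baseline factors against PFS is Table 53, in an optional annex. That table compares patients with PFS of at least 9 months (7) with the rest (27) by t-test, Mann-Whitney or Fisher test.

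**The concern.** A log-rank test compares groups. Age, time since diagnosis, Barthel index and mini-mental score are collected as numbers, so to use 10.4 on them someone must choose a cut. Cutting discards information, and a cut that is not written down can be chosen after the data are seen.

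The usual log-rank p-value also relies on a large-sample approximation, which is weakest when one group holds a handful of patients. If an alteration is present in only 1-4 patients, the approximation can declare significance too often, and mostly in one direction: a carrier who happens to progress or die early makes the marker look adverse. Relating the markers to PFS and OS is a named objective, so such a result could well be reported.

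**Working it through.** **Inputs.** Planned size from section 10.3: "Sample size: 40 patients". The SAP shells use 34. 6-month PFS is 25% or 45% (section 10.3), MRI every 12 weeks (8.3), recruitment 28 months and follow-up 6 months (3.7). Assumed, because the documents are silent: a two-sided 5% level for these tests, the number of carriers, and the strength and shape of continuous effects.

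**The plan's own figure.** Section 10.4 states none. The sample size it works with can be reproduced from 10.3 by the two-sided normal approximation:
[1.960·√(0.25·0.75) + 0.842·√(0.45·0.55)]² / 0.20² = (0.849 + 0.419)² / 0.04 ≈ 40.2.

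**Rare marker: a case that can be checked by hand.** Take n = 40, one carrier, everyone has the event, no ties. If the carrier is the r-th to fail, with h_j = 1/(40−j+1):
U = 1 − Σ h_j, V = Σ h_j(1−h_j), both summed over j = 1..r; reject if U²/V > 3.84.

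| Carrier's rank r | 1 | 2 | 3 | 4 | 5 | 6 | 7 | 39 | 40 |
|---|---|---|---|---|---|---|---|---|---|
| U²/V | 39.0 | 18.3 | 11.4 | 7.9 | 5.9 | 4.5 | 3.6 | 1.95 | 4.04 |

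Under the null every rank is equally likely. Ranks 1-6 reject as worse and rank 40 as better, so the size is 7/40 = 17.5%, of which 6/40 = 15% is on the worse side. Enumerating all pairs for two carriers gives 76 worse and 7 better out of 780, or 83/780 = 10.6%. For three carriers it is 761 and 125 out of 9,880, or 886/9,880 = 9.0%.

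**Simulated size of the 5% asymptotic test, n = 34-40.**

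| Carriers | Untied times | PFS tied exactly at 12-week scans |
|---|---|---|
| 1 | 14-18% | 0.6-3.2% |
| 2 | 10-11% | 2.0-6.2% |
| 3 | 8-9% | 4.5-6.6% |
| 4 | 7-8% | 5.3-6.6% |
| 6 or more | about 6-7% | 5.2-5.9% |

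The untied column fits OS. With random censoring (60-85% events), the split between worse and better is 9.3-9.6% against 0.4-1.0% for 2 carriers, and 6.2-6.6% against 1.0-1.4% for 4.

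The tied column is lower because early failures share one time. At 6-month PFS of 25%, survival at the first scan (12 weeks = 2.76 months) is 0.25^(2.76/6) = 0.53, so about 19 of 40 progress there. A single carrier among them gives (1−19/40)² / [19·(1/40)·(39/40)·(21/39)] = 0.276/0.249 = 1.1, far short of 3.84.

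Real PFS lies between the columns. Spreading scan dates by ±10 days gives 14%, 10.6-10.8% and 8.6-8.8% for 1, 2 and 3 carriers. Keeping exact ties but placing 20% of progressions between scans gives about 8%, 7.3-7.5% and 7.0-7.1%. The date spread and the between-scan share are assumptions.

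**Continuous factor: power with the factor kept continuous, minus power of the log-rank after a median split** (normal factor, 60-100% events, n = 34-40).

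| HR per SD | 1.35 | 1.49 | 1.65 | 1.82 | 2.0 |
|---|---|---|---|---|---|
| Points lost | 7-13 | 12-19 | 17-20 | 17-21 | 13-22 |

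For example, with n = 40 and 85% events, power is 57%, 74% and 87% continuous against 40%, 54% and 67% split, at 1.49, 1.65 and 1.82. A 75/25 split loses 5-23 points over the whole range.

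**Does the remedy work?** The permutation log-rank at n = 40 rejects in 2.8%, 5.1%, 4.3%, 5.0% and 4.7% of null trials with 1, 2, 3, 6 and 10 carriers.

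**The case against.** The strongest reply is that the size inflation depends on things the documents do not say. Section 10.4 does not mention biomarkers, sets no 5% level for these tests (the 0.05 in 10.3 belongs to the primary hypothesis) and does not choose the asymptotic p-value, so a permutation log-rank would already comply. Carrier counts of 1-4 are nowhere stated. At the frequencies that are quoted, more than a third for CDKN2A (about 13 of 40) and 15-20% for CDK4 in glioblastoma (6-8 of 40), the size is only about 5-7%. All of this stands. The enrichment of CDKN2A deletion in tumours this trial excludes may lower that count, but no figure is given.

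The reply also points to scan-tied PFS, where the test is near or below nominal for 1-2 carriers and the adverse bias is absent. That holds for exact ties only. Sections 8.3 and 8.7 and Annex IV advise repeat imaging on neurological worsening or a higher dexamethasone need, and count clinical deterioration as progression, so some dates will fall between scans. OS is not scan-tied at all.

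On continuous factors, the reply is that SAP Table 53 leaves age, Barthel, mini-mental and time from diagnosis uncut. True, but it splits PFS at 9 months instead, is optional and does not cover OS. It does not replace 10.4. Barthel and mini-mental are bounded scores, so the normal-factor figures are only a guide for them.

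A reader might infer that the log-rank test governs every association in the trial, or that its error rate is inflated for the biomarkers in general. The documents support neither: the response-rate objective lies outside 10.4, the SAP uses other tests, and the inflation needs few carriers and largely untied times.

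**Conclusion.** The point holds in a limited form. As the only named test for PFS and OS, the log-rank fits continuous factors poorly, and it carries an unstated choice of cut-points. The power cost is about 7-13 points at a hazard ratio of 1.35 per SD and 12-22 points at about 1.5-2.0, assuming a roughly normal factor and a median split.

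For the biomarkers, the concern is conditional on reading 10.4 as covering them, on 1-4 carriers, on the asymptotic p-value and on a conventional 5% level. Then the real size is about 14-18% falling to 7-8% for OS or untied PFS, mostly as false adverse findings. If any of those conditions fails, or if PFS is tied exactly at the scans, most of the inflation goes. With one or two carriers no test will be informative, and an honest p-value mainly prevents over-reading.

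These are exploratory secondary analyses in a single-arm pilot, and no decision rule depends on them. Priority: minor to moderate.

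**What to change.** In section 10.4 and the SAP:

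- State that the five markers of section 4.6.2 are analysed against PFS and OS.
- For age, time since diagnosis, Barthel index and mini-mental score, use univariable Cox regression on the continuous scale, reporting the hazard ratio per stated unit with its 95% CI.
- For binary factors and the named biomarkers, use the permutation log-rank p-value and print the number of carriers beside it.

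The cost is two or three sentences and a few lines of code, with no new data. There are two downsides: the Cox model assumes a log-linear effect, and p-values for rare markers will be less favourable than the asymptotic ones.

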11. ETHICAL AND LEGAL CONSIDERATIONS

11.1. Ethics Committee

The study will be carried out in accordance with the principles of the Declaration of Helsinki Adopted by the 18th World Medical Assembly, Helsinki, Finland, June 1964 updated to its latest version Fortaleza, Brazil, October 2013.

With the standards of Good Clinical Practice (GCP) issued by the working group on the Efficacy of Medicinal Substances of the European Economic Community (1990) (CPMP/ICH/135/95).

And the Laws and Regulations in force in Spain:

- Royal Decree 1090/2015, of December 4, which regulates clinical trials with medicines, the Ethics Committees for Research with medicines and the Spanish Registry of Clinical Studies.
- The Oviedo Convention of April 4, 1997 on human rights and biomedicine, ratified in the BOE in October 1999.
- In the rules for the adequate protection of personal data, as provided in Regulation (EU) 2016/679 of the European Parliament and of the Council of April 27, 2016 regarding the protection of natural persons with regard to processing of personal data and the free circulation of these data and repealing the European Parliament Directive 95/46/EC of October 24, 1995 on the protection of individuals with respect to the processing of personal data and Organic Law 3 /2018 on Protection of Personal Data and guarantee of digital rights. The rights and obligations regarding clinical information and documentation, as provided in Law 41/2002, of November 14, the basic regulator of patient autonomy.
- Law 14/2007, of July 3, on Biomedical Research.

11.2. Authorities

The study protocol and/or documents inherent to it will be sent to them before starting the trial, as established by national authorities.

11.3. Informed consent

The patient must sign two separate informed consents: one for the clinical trial, another for biological samples.

The doctor will have to explain the nature, purposes and possible consequences of the clinical trial, in a way that is understandable to the patient.

The subject of the study will give his or her consent by signing the corresponding model in duplicate. For this purpose, each model must bear the signature of the researcher and the patient.

The investigator will not initiate any determination corresponding to the trial until the patient's consent has been obtained.

The informed consent used in the trial and any changes made during the study must be approved by the Ethics Committee.

11.4. Confidentiality

In order to guarantee the confidentiality of the trial data in accordance with the provisions of Organic Law 3/2018 on the Protection of Personal Data and guarantee of digital rights and Regulation (EU) 2016/679 of the European Parliament and of the Council of 27 of April 2016 relating to the protection of natural persons with

regard to the processing of personal data and the free circulation of these data and repealing the European Parliament Directive 95/46/EC of October 24, 1995 on the protection of people with respect to the processing of personal data, only the personnel designated by the Promoter, for monitoring/auditing tasks, the researcher and his team of collaborators, the Clinical Research Ethics Committee of the corresponding center will have access to them. or the one who oversees the trial and the relevant health authorities.

In the aforementioned case of Monitoring/Audits, the researcher must provide direct access to the source documents and data.

The content of the data collection notebooks (CRD) as well as the documents generated during the study will be protected from unauthorized uses by people outside the research and, therefore, will be considered strictly confidential and will not be revealed to third parties except those specified in the previous section.

11.5. Safe

All patients in this clinical study will be insured through an insurance policy, in compliance with the conditions stipulated by the R.D. 1090/2015 of December 4 and European Regulation 536/2014 of April 16, which regulate clinical trials with medicines.

11.6. End of study

The trial will be considered regulatory closed after the primary and secondary endpoints are sufficiently prepared for initial publication. Follow-up observations of patients included in the trial can be maintained indefinitely.

11.7. Premature end of study

This study may be stopped prematurely if, in the opinion of the sponsor, there is sufficient reasonable cause. The investigator will receive written notification in which the terminated party documents the reason for discontinuing the study.

Circumstances justifying study discontinuation include, but are not limited to:

- Determination of unforeseen, considerable or unacceptable risks to patients
- Impossibility of including an acceptable number of patients
- Insufficient compliance with protocol requirements
- Plans to modify, suspend or discontinue the development of the study drug.

In the event of premature termination of the study, all materials (fully or partially completed and blank CRDs, study drug, etc.) must be returned to the Sponsor.

12. PRACTICAL CONSIDERATIONS

12.1. Diagnostic Criteria for the Pathology Under Study

Patients with confirmation of the diagnosis of Anaplastic Oligodendroglioma (OA) in the Pathological Anatomy Service of the 12 de Octubre University Hospital [REDACTED] that will also determine if there is nuclear expression of the RB protein through immunohistochemistry, and who comply with the criteria, may be included in this study. the eligibility criteria detailed in point 6 of this protocol.

12.2. Researcher Responsibilities According to Good Clinical Practices

The responsibilities of the principal investigator in each participating Center will be:

1. Sign the essay project.
2. Know in depth the properties of medications.
3. Obtain informed consent from subjects prior to inclusion in the trial.
4. Ensure that patients will receive appropriate medical care in case of adverse events, including significant laboratory values related to the assay.
5. Collect, record and report data correctly.
6. Immediately report serious or unexpected adverse events to the sponsor.
7. Guarantee that all people involved will respect the confidentiality of any information about the test subjects.
8. Regularly inform the Clinical Research Ethics Committee of the progress of the trial.
9. Be responsible for preparing the final report of the test, giving your agreement to it with your signature.

12.3. Instructions for completing the CRD

The CRD completion guide is located in the center's researcher file.

12.4. Supply of study medication

Palbociclib will be supplied by the Promoter through the Pfizer SLU laboratory.

12.5. Conditioning and Labeling

Labels of study drugs will contain information that complies with applicable regulatory requirements.

12.6. Articles and Publications

As indicated in Royal Decree 1090/2015 of December 4 and European Regulation 536/2014 of April 16, which regulate clinical trials with medicines, the promoter is obliged to publish both positive and negative results. negative results, from clinical trials authorized in scientific journals and with mention of the Clinical Research Ethics Committee that approved the study.

The Responsible Investigators of the study and the researchers who contribute at least 3% of the patients will appear as authors.

The order of authors will be strictly based on the number of patients included by the different researchers.

The clinical publication will be carried out by those responsible for the clinical study and the clinical researchers. It will be the responsibility of the first author, the Principal Investigators of the study, and the study designer to write the final publications.

The anonymity of the subjects who are the source of the study samples will be maintained at all times. The results or conclusions of the study will be communicated primarily in scientific publications before being disclosed to the non-health public. Procedures of as yet undetermined effectiveness will not be made known in a premature or sensational manner.

Participating investigators should not publish any data about patients that are directly related to the objectives of the study until the trial report is published.

The trial will be registered in the public access database, www.clinicaltrials.gov and, according to the provisions of Royal Decree 1090/2015 of December 4 and European Regulation 536/2014 of April 16, which regulate clinical trials with medicines, in the Spanish Registry of Clinical Studies (REec).

